#### *Radiological outcomes*

Radiological outcomes will be defined in a separate imaging protocol.

#### *Health-economic variables:*

Costs related to:

- Length of hospital stay
- Nursing home care after discharge
- Re-hospitalisations during first 3 months

## 11. Analysis and statistical considerations

### 11.1 Estimation of sample size

It is uncertain whether the difference in treatment effect between thrombolysed and non-thrombolysed wake-up stroke patients will be similar to that of stroke patients with known time of onset. We originally based our sample size estimation on the results of a Cochrane systematic review of the effect of rt-PA within 4.5 hours of stroke onset, assessed as a binary endpoint (favourable outcome mRS 0-2 versus mRS 3-6). As the primary endpoint in TWIST is mRS across the full ordinal scale (shift analysis), sample size estimation based on ordinal logistic regression analysis is more appropriate.

Longer time from stroke onset to treatment in wake-up stroke patients compared to patients with known symptom onset is anticipated and this is likely to weaken the treatment effect. However, recent trials on patients with wake-up strokes found similar and actually larger differences between thrombolysed and non-thrombolysed patients with wake-up stroke/unknown stroke onset time. In the largest randomized controlled trial on wake-up strokes, WAKE-UP, with favourable outcome defined as mRS 0-1, the difference between thrombolysed and non-thrombolysed patients was 11.5%. The same difference of 11.5% was also found in a recent meta-analysis of 6 observational studies on patients with unknown stroke onset time, where favourable outcome was

defined as mRS 0-2. The MRI-based inclusion criteria in WAKE-UP compared to the CT-based inclusion in TWIST could lead to a smaller treatment effect in TWIST. Furthermore, selection bias in observational studies may result in larger treatment effect than in randomised-controlled trials. It is therefore possible that the effect size in TWIST will be closer to the observed effect in recent studies on wake-up stroke patients than to the effect in previous studies on patients with known time of symptom onset and that the mRS distribution in the control group differs from early trials of IV thrombolytic treatment.

Based on these observations, we assume a treatment effect of 10% absolute difference in a binary endpoint setting (mRS 0-1 versus mRS 2-6) and a distribution between modified Rankin Scale categories similar to that of WAKE-UP with 42% with favourable outcome in the non-thrombolysed group vs 52% in the thrombolysed group, which corresponds to an odds ratio of 1.50. We assume a mRS distribution in the control group in six levels (categories 5 and 6 merged) as 15%, 27%, 23%, 17%, 13%, 5%, (similar to the control group the WAKE-UP trial). With a power of 80%, a two-sided significance level of 5%, and an effect size specified as an odds ratio of 1.50 from an ordinal logistic regression model, the estimated sample size is 600. Based on this, the revised target is to recruit 600 patients, i.e. 300 patients in each arm.

## 11.2 Statistical analyses

A detailed Statistical Analysis Plan has been drawn up and will be published before breaking the randomisation code. We will analyse the data according to the intention-to-treat principle. Functional outcome will be primarily compared between the study groups by means of ordinal logistic regression, after adjustment for covariates. In a secondary analysis, functional outcome will be dichotomised (mRS score 0-1 vs. 2-6) and analysed by means of logistic regression.

For clinical events we will estimate odds ratios and 95% confidence intervals using logistic regression and estimate hazard ratios and 95% confidence intervals using the Cox proportional hazards model, as appropriate. Interactions will be tested using likelihood ratio tests. The risks of clinical events will be compared using Kaplan-Meier survival analyses and log-rank tests. All analyses will use 5% two-sided level of significance.

We will perform prespecified subgroup analyses of patients with findings suggestive of penumbra (on CT perfusion), of patients included based on presence or absence of DWI/FLAIR mismatch on MRI, of patients with proximal cerebral artery occlusion, and of patients with different time intervals since awakening, controlling for imbalances in baseline characteristics. Subgroup analyses will be prespecified in the Statistical Analysis Plan. Patients treated with intra-arterial intervention for proximal cerebral artery occlusion will also be analysed separately, and the primary effect variable for this analysis will be cerebral arterial patency before intra-arterial intervention.

Any missing components of the baseline NIHSS will be imputed using a regression-based technique, using age and all other components of the NIHSS. A worst-case approach will be used when handling incomplete dates and times for adverse events. For example, events will be assumed to be treatment emergent unless it is clear even from the partial date/time that this is not the case.

As subgroup analyses are of an exploratory nature, no adjustment for multiple comparisons will be made.

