**Data from clinical studies**

Tenecteplase is preferred over alteplase for treatment of myocardial infarction, because it has lower risk of bleeding complications, and because of the pharmacological advantages listed above.

A number of observational studies in patients with ischaemic stroke have shown that, compared to alteplase, tenecteplase is associated with similar or better recanalisation rates and clinical outcomes, and a similar or lower risk of intracranial haemorrhage. These studies have also concluded that the optimal dose of tenecteplase for stroke is 0.25 mg/kg.

[figure not shown]
There has also been three small randomised-controlled trials of tenecteplase vs. alteplase in acute ischaemic stroke. Meta-analysis of these trials with a total of 283 patients have shown that 76/178 patients (43%) patients given tenecteplase (doses ranging from 0.1 to 0.4 mg/kg) achieved good functional outcome (mRS score 0-1), compared to 33/105 patients (31%) patients given alteplase (odds ratio (OR) 1.39, 95% confidence interval (CI) 0.82-2.36, Figure 1).

**Figure 1.** Good functional outcome (mRS score 0-1) at three months

[figure not shown]

There was also a non-significant lower risk of symptomatic intracranial haemorrhage in patients given tenecteplase (Figure 2). The risks were 7/131 (5%) in patients given tenecteplase and 4/56 (7%) in patients given alteplase (OR 0.71, 95% CI 0.11-4.42). ATTEST 2014 did not provide data on symptomatic intracranial haemorrhage.

**Figure 2.** Symptomatic intracranial haemorrhage

There was no significant difference in the risk of death at three months (Figure 3). In total, 24 of the 178 patients (13%) given tenecteplase and 17 of the 123 patients (14%) given alteplase were dead at three months (OR 1.00, 95% CI 0.52-1.95).

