### 10.2 Secondary effect variables

#### *Clinical events:*

- Any intracranial haemorrhage during follow-up
- Symptomatic intracranial haemorrhage by SITS-MOST definition
- Symptomatic intracranial haemorrhage by IST-3 definition
- Parenchymal haemorrhage type 2Stroke progression during follow-up
- Recurrent ischaemic stroke during follow-up
- Major extra cranial bleeding
- Death from all cause during follow-up

Clinical events are defined in the Appendix.

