### 16.2.3 Recurrent stroke

Neurological deterioration (increase of  $\geq 2$  on NIHSS, after exclusion of other causes for neurological deterioration) occurring after 72 hours will be considered as a recurrent stroke. Recurrent stroke will be classified as ischaemic, haemorrhagic or unknown (if not documented on imaging).

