### 16.2.4 Symptomatic intracranial haemorrhage (SICH)

The IST-3 and SITS-MOST definition of symptomatic intracranial haemorrhage are used:  
**SICH per IST-3:** symptomatic intracranial haemorrhage is defined as clinically significant deterioration (neurological deterioration, new headache, new acute hypertension, new nausea or vomiting, or sudden decrease in conscious level) or death within the first seven days of treatment with evidence of either significant brain parenchymal haemorrhage (local or distant from the infarct) or significant haemorrhagic transformation (HT) of an infarct on brain imaging.  
**SICH per SITS-MOST:** SICH is defined as local or remote parenchymal haematoma type 2 on the imaging scan obtained 22-36 hours after treatment, plus neurological deterioration, as indicated by an increase in National Institutes of Health Stroke Scale (NIHSS) score of  $\geq 4$  points compared to baseline value or the lowest value between baseline and 24 ( $\pm 6$ ) hours, or haemorrhage leading to death.

**Parenchymal haematoma type 2** indicates a haematoma exceeding 30% of the infarct, with obvious mass effect.

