11.2 Statistical analyses

A detailed Statistical Analysis Plan will be drawn up before breaking the randomisation code. We will analyse the data according to the intention-to-treat principle. Functional outcome will be primarily compared between the study groups by means of ordinal logistic regression, after adjustment for covariates. In a secondary analysis, functional outcome will be dichotomised (mRS score 0-1 vs. 2-6) and analysed by means of logistic regression.

For clinical events we will estimate odds ratios and 95% confidence intervals using logistic regression and estimate hazard ratios and 95% confidence intervals using the Cox proportional hazards model. Interactions will be tested using likelihood ratio tests. The risks of clinical events will be compared using Kaplan-Meier survival analyses and log-rank tests, after adjustment for confounding variables. All analyses will use 5% two-sided level of significance.

We will perform prespecified subgroup analyses of patients with findings suggestive of penumbra (on CT perfusion), of patients included based on presence or absence of DWI/FLAIR mismatch on MRI, of patients with proximal cerebral artery occlusion, and of patients with different time intervals since awakening, controlling for imbalances in baseline characteristics. Subgroup analyses will be prespecified in the Statistical Analysis Plan. Patients treated with intra-arterial intervention for proximal cerebral artery occlusion will also be analysed separately, and the primary effect variable for this analysis will be cerebral arterial patency before intra-arterial intervention.

Any missing components of the baseline NIHSS will be imputed using a regression-based technique, using age and all other components of the NIHSS. A worst-case approach will be used when handling incomplete dates and times for adverse events. For example, events will be assumed to be treatment emergent unless it is clear even from the partial date/time that this is not the case.

As subgroup analyses are of an exploratory nature, no adjustment for multiple comparisons will be made.

12. Trial conduct and practices/procedures

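### Kaplan-Meier with deaths censored slightly overstates the absolute 90-day risk of events that death can pre-empt, chiefly recurrent ischaemic stroke

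*Protocol*

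**What the plan says.** Section 11.2 of the Protocol plans several analyses of clinical events. It begins with regression models: "For clinical events we will estimate odds ratios and 95% confidence intervals using logistic regression and estimate hazard ratios" (the latter from Cox models, each used where suitable). It then adds: "The risks of clinical events will be compared using Kaplan-Meier survival analyses and log-rank tests". The Combined protocol and SAP, an earlier version, names the same method: "The risks of clinical events will be compared using Kaplan-Meier survival analyses and log-rank tests, after adjustment for confounding variables".

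Section 10.2 of the Protocol lists the events. They include intracranial haemorrhage under several definitions, stroke progression, major extracranial bleeding and "Recurrent ischaemic stroke during follow-up". Mortality is a separate item: "Death from all cause during follow-up". Follow-up is a fixed 3 months (section 9).

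Two definitions in the appendix matter here. Section 16.2.3 says that deterioration "occurring after 72 hours will be considered as a recurrent stroke". Section 16.2.4 counts clinical deterioration "or death within the first seven days of treatment", with haemorrhage on imaging, as symptomatic haemorrhage under the IST-3 definition. The SITS-MOST definition also includes haemorrhage that leads to death.

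Neither document mentions competing risks, cumulative incidence or cause-specific analysis. Section 11.2 refers to a detailed Statistical Analysis Plan, whose text was not available for this review.

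**The concern.** A patient who dies without a recurrent stroke can no longer have one. The usual Kaplan-Meier analysis of time to recurrent stroke treats that death as censoring. The survivors then stand in for the dead patient, as if he or she were still at risk. The curve therefore estimates the risk in a setting where nobody dies, and this is at least as high as the proportion of randomised patients who actually have the event within 90 days.

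The error always has the same sign, and recruiting more patients does not reduce it. It also grows with mortality, so arms with different mortality are inflated by different amounts. What is at stake is any absolute risk, or difference in absolute risks, read from such a curve and published as the 90-day risk.

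**Working it through.** The plan states no expected risk for these events, so there is no figure of its own to reproduce. The sample size of 600 rests on the mRS and plays no part here.

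**Inputs from the documents**
- Follow-up is 90 days.
- Deaths by 3 months in earlier trials (section 3.2) were "24 of the 178 patients (13%) given tenecteplase" and 17 of 123 (14%) given alteplase.
- The control assumption in section 11.1 puts mRS 5 and 6 together at 5%, so assumed control deaths are at most 5%.
- Each arm has 300 patients.
- For scale, symptomatic haemorrhage in earlier trials was 5% to 7% (section 3.2).

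**Assumptions**
- The true 90-day event risk I is 5%.
- The timing of events and deaths is as shown in the table.
- D is the proportion who die without the event. Using all-cause mortality for D slightly overstates it.

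**Formula.** Let F(t) and G(t) be the cumulative incidences of the event and of death without it. With deaths censored,

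1 − KM = 1 − exp(−∫ dF / (1 − F − G)).

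Under constant hazards this becomes 1 − exp(ln(1 − I − D) × I/(I + D)).

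- D = 5%: ln(0.90) × 0.05/0.10 = −0.0527, giving 5.13%.
- D = 14%: ln(0.81) × 0.05/0.19 = −0.0555, giving 5.39%.

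**One minus Kaplan-Meier when the true risk is 5.00%**

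| Timing of event; timing of deaths | 5% die | 10% die | 14% die |
|---|---|---|---|
| Constant hazards, 90 days | 5.13% | 5.27% | 5.39% |
| Days 3–90, even; deaths even | 5.14% | 5.28% | 5.41% |
| Days 3–90, even; deaths early (mean 14 days) | 5.23% | 5.48% | 5.70% |
| First 7 days; deaths early | 5.05% | 5.11% | 5.16% |
| First 7 days; deaths even | 5.01% | 5.02% | 5.03% |
| First 36 hours; deaths even | 5.00% | 5.00% | 5.01% |

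The second and third rows represent recurrent stroke, which counts only after 72 hours. The last three represent early haemorrhage. With deaths raised to 20%, beyond anything in the documents, the excess for an event confined to 7 days is still only 0.23 points.

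**Simulation.** For the third row, 4,000 simulated arms of 300 patients gave mean Kaplan-Meier risks of 5.26%, 5.49% and 5.68%. The simple proportions averaged 5.03%, 5.01% and 4.98%, so the proportion recovers the true risk.

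**False difference between arms with equal true risks of 5%**
- Deaths 13% and 14%, constant hazards: about 0.03 points.
- Deaths 5% and 14%, early: 5.70 − 5.23 = 0.47 points.
- Standard error of the difference: √(2 × 0.05 × 0.95/300) = 1.78 points.

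**The case against.** The strongest reply is that Kaplan-Meier is only one of the planned analyses. Logistic regression on all randomised patients over a fixed follow-up does not censor deaths. Log-rank and Cox remain valid comparisons of cause-specific hazards. The sentence at issue speaks of comparing risks, and nothing says that the Kaplan-Meier value at day 90 will be the published risk. Kaplan-Meier is also the right method for all-cause death, which is on the same list. The detailed Statistical Analysis Plan may already deal with deaths. All of this stands, and it confines the point to absolute risks taken from the curves.

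Three stronger readings are tempting, and the documents do not support them.

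- A reader might infer that every safety risk other than death is materially inflated. Symptomatic haemorrhage under IST-3 is limited to 7 days, and under SITS-MOST it rests on imaging at 22 to 36 hours. Few deaths can come first, and fatal haemorrhage already counts as an event.
- A reader might infer that equal true risks will visibly differ between arms. That needs a large mortality difference, and a split of 5% versus 14% has no source in the documents. Even then the false difference is about a quarter of one standard error (0.47/1.78 = 0.26).
- A reader might infer that the trial will see 13–14% mortality. Those figures come from earlier trials of tenecteplase against alteplase. The plan's own control assumption allows at most 5%.

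The reply leaves one gap. The regression models do not supply the absolute risks that a Kaplan-Meier curve shows, and the text does not say how deaths enter that curve.

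**Conclusion.** The point holds as a minor improvement that costs nothing. For events that death can pre-empt and that can occur throughout follow-up, chiefly recurrent ischaemic stroke and late extracranial bleeding, one minus Kaplan-Meier with deaths censored overstates the 90-day risk. The excess on a 5% risk is about 0.1 to 0.2 points at 5% mortality and 0.4 to 0.7 points at 14%. For early haemorrhage it is negligible or close to it, and the effect on the comparison of arms is far below sampling error.

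The direction follows from the method. The size rests on the assumed 5% risk, the assumed timing and the mortality range. Censoring at death is implied by the method; the documents do not state it. The primary analysis and the sample size are not affected.

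**What to change.** In section 11.2, or in the Statistical Analysis Plan if it does not already cover this:

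- Report absolute 90-day risks of events other than death as simple proportions of randomised patients. Where follow-up is incomplete, use Aalen-Johansen cumulative incidence with death as a competing event.
- Label the Cox and log-rank results for these events as cause-specific, and state that deaths are censored in them.
- Keep Kaplan-Meier for all-cause death.

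The cost is one or two sentences and a standard software option, settled before the randomisation code is broken. It needs no new data. If the Statistical Analysis Plan already specifies this, a cross-reference in section 11.2 is enough.

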## **6.2 Non-contrast CT and CT angiography for patient screening before randomisation**

All patients should be screened with non-contrast CT, and CT angiography should be performed, if possible. Findings on non-contrast CT shall only be used to exclude patients who are unlikely to benefit from treatment (See Exclusion criteria in Section 5). If other, advanced imaging examinations are used (see sections 6.3 and 6.4, below), findings on such examinations shall not influence the decision to include the patient, unless the results of such imaging show that the patient should or should not receive thrombolytic treatment, in the opinion of the investigator.

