## **8. Trial treatment**

Patients will be randomly allocated to open-label tenecteplase plus best standard care or to best standard care alone.

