### **8.3 Best standard care and other treatments**

Both arms will receive best standard care, including intra-arterial interventions for proximal cerebral artery occlusion. If the patient is given tenecteplase, then aspirin or other antiplatelet or anticoagulant drugs shall not be given until 24 hours after termination of infusion and after the control CT brain scan. If the patient was allocated to control, he/she will receive aspirin 300 mg as a loading dose as soon as possible after randomisation. After the first 24 hours the recommended daily dose of aspirin is 75 mg once daily in both the tenecteplase group and the control group. Best standard care during the first week also includes treatments to maintain normal homeostasis (temperature, blood glucose, hydration, nutrition), as well as lipid lowering and blood pressure lowering drugs, in accordance with clinical guidelines. Clinical examinations, including additional CT scans will be performed as clinically indicated.

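### The intra-arterial patency analysis uses a set chosen after open-label allocation; section 11.2 should fix the set before randomisation and say how unobserved patency is handled

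*Protocol*

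**What the plan says.** Protocol section 11.2 lists subgroup analyses, among them "of patients with proximal cerebral artery occlusion, and of patients with different time intervals since awakening". It does not say when, or on which scan, occlusion is established. It then adds a further analysis: "Patients treated with intra-arterial intervention for proximal cerebral artery occlusion will also be analysed separately". Its outcome is named directly afterwards, in these words: "the primary effect variable for this analysis will be cerebral arterial patency before intra-arterial intervention". The same section adopts intention-to-treat, states "All analyses will use 5% two-sided level of significance", and closes with "As subgroup analyses are of an exploratory nature, no adjustment for multiple comparisons will be made".

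On timing, section 8 says "Patients will be randomly allocated to open-label tenecteplase plus best standard care or to best standard care alone" and section 8.3 says "Both arms will receive best standard care, including intra-arterial interventions for proximal cerebral artery occlusion". The intervention is therefore part of care given after allocation. No section says how or when referral is decided.

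On imaging, section 6.2 says that before randomisation "CT angiography should be performed, if possible". Table 2 schedules no vessel scan between randomisation and 24±6 hours, and section 9.1 limits that later angiography to patients with a positive baseline angiogram. Section 8.3 allows extra CT scans where clinically indicated, and section 6.3 sends all trial CT scans for central blinded reading.

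Patency is not named as an effect variable in sections 10.1 or 10.2, which leave radiological outcomes to a separate imaging protocol. Neither that protocol nor the standalone SAP mentioned in section 11.2 is in the supplied text. The document headed Combined protocol and SAP is an earlier protocol version, and its section 11.2 has the same two sentences on the intra-arterial analysis.

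**The concern.** Two features combine. Membership of the set is settled after randomisation, by clinicians who know the arm. The outcome, an artery already open, is also itself a reason not to intervene. Who enters can therefore depend on early reopening, on clinical improvement and on the known arm, and the patients left in the two arms need not be comparable.

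Analysing by allocated arm does not repair this, because the problem is the set and not the labels. Blinded image reading and blinded follow-up do not help either, because the selection happens at referral.

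What is at stake is a statement about early reopening with tenecteplase. Section 11.2 gives this analysis its own primary effect variable, so a difference between arms is likely to be read as a drug effect.

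**Working it through.** **1. The plan's own figures.** The documents give no size, rate or power for this analysis. The one related figure is the total of 600 in section 11.1, checked here only to show that the point does not touch it. The inputs are a common odds ratio of 1.50, 80% power, 5% two-sided, and control mRS proportions of 15, 27, 23, 17, 13 and 5%. The Whitehead formula gives N = 12(1.960 + 0.842)² / [(ln 1.50)² × (1 − Σp̄³)] = 600.8, where p̄ is the mean of the two arms' proportions. The stated 600 reproduces, and nothing below enters it.

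**2. Selection formula.** Among patients with a proximal occlusion at baseline, let p be the true share open before any intervention, f the share of reopened patients who do not enter the set, and g the share of still-occluded patients who do not enter it. Then

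- seen patency = p(1−f) / [p(1−f) + (1−p)(1−g)]
- seen OR = true OR × [(1−fT)/(1−fC)] × [(1−gC)/(1−gT)], with T for tenecteplase and C for control.

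**3. Illustration.** All rates are assumed. True patency is 20% versus 5%, so the difference is 15 points and the OR is (0.20/0.80)/(0.05/0.95) = 4.75.

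| Not in the set, tenecteplase/control | Seen patency | Seen OR |
|---|---|---|
| reopened 15%/5% | 17.5% vs 4.8% | 4.75 × 0.85/0.95 = 4.25 |
| reopened 5%/15% | 19.2% vs 4.3% | 4.75 × 0.95/0.85 = 5.31 |
| reopened 30%/10% | 14.9% vs 4.5% | 4.75 × 0.70/0.90 = 3.69 |
| reopened 10%/30% | 18.4% vs 3.6% | 4.75 × 0.90/0.70 = 6.11 |
| occluded 10%/5% | 21.7% vs 5.2% | 4.75 × 0.95/0.90 = 5.01 |
| occluded 5%/10% | 20.8% vs 5.5% | 4.75 × 0.90/0.95 = 4.50 |
| occluded 20%/10% | 23.8% vs 5.5% | 4.75 × 0.90/0.80 = 5.34 |
| occluded 10%/20% | 21.7% vs 6.2% | 4.75 × 0.80/0.90 = 4.22 |

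Equal loss of reopened patients keeps the OR at 4.75, but the difference falls from 15 points to 13.2 (15% in both arms) or 11.3 (30% in both). With no drug effect (10% in each arm), reopened losses of 15%/5% and 5%/15% give OR 0.89 and 1.12; 30%/10% and 10%/30% give 0.78 and 1.29.

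**4. Literal and milder readings.** Choosing patency before the intervention as outcome implies that a patient found open at the first procedural angiogram still counts as treated, but no section says so. If such patients count, only those never taken to angiography are lost. If they do not, f is larger. If reopened patients enter half as often, or twice as often, in the tenecteplase arm as in control, the OR becomes 4.75 × 0.5 = 2.38 or 4.75 × 2 = 9.50. If f is 100% in both arms, seen patency is 0% in both and no effect can be estimated.

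**5. Scale.** With an assumed 50 patients per arm, the SE of log OR is √(1/10 + 1/40 + 1/2.5 + 1/47.5) = 0.739, so the 95% interval around 4.75 is about 1.1 to 20.2. Every shifted odds ratio for the 20% versus 5% case lies inside it.

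**6. What a baseline set can deliver.** Now let f and g be the shares without early vessel imaging. The bounds per arm are p(1−f) and p + (1−p)g. Bounds on the difference set opposite extremes in the two arms, and their width is the sum of the two unobserved shares.

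- f = 10%, g = 5% (6.0% and 5.25% unobserved): 18.0–24.0% versus 4.5–9.75%, difference 8.25 to 19.5 points.
- f = g = u in both arms: the lower bound is 0.15 − 1.15u, which reaches zero at u = 13.0%.
- f = 50%, g = 20% (26.0% and 21.5% unobserved): 10.0–36.0% versus 2.5–24.0%, difference −14.0 to 33.5 points, which is uninformative.

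**The case against.** The strongest reply is that changing the set gains little. If arteries open at the first angiogram already count and no other early scan is scheduled, the patients with observed patency are largely the same as before, and only bounds are added. That stands. A reader might infer that the occlusion subgroup avoids the selection; it does not. It turns the selection into missing outcome data that can be counted by arm. That is still a gain over a set in which the losses cannot be seen.

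The definition may also sit in the SAP or the imaging protocol, and a protocol sentence need not carry this detail. That stands too, and limits the request.

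Four further inferences go beyond the text:

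- That section 11.2 lists a baseline occlusion subgroup. It names occlusion without timing or modality; fixing it before randomisation is a proposal that section 6.2 makes possible.
- That the plan declares this analysis exploratory. The closing sentence of section 11.2 names subgroup analyses, and this one is introduced as additional.
- That a between-arm test on the treated set is planned. Only the general 5% statement could cover it.
- That intention-to-treat is breached. Analysis by allocated arm is not contradicted.

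**Conclusion.** The point holds and is minor. Receipt of the intervention follows open-label allocation and can depend on the outcome and on the arm, so a between-arm comparison of patency in treated patients could mis-state the effect on early reopening in either direction. Neither size nor direction can be derived from the documents. The illustrations rest wholly on assumed patency and referral rates, and at an assumed 50 patients per arm the shifts are small beside sampling error. The primary mRS analysis and the target of 600 are untouched. The conclusion is conditional on the absent SAP and imaging protocol not already defining the set.

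**What to change.** In section 11.2, with matching text in the SAP before the randomisation code is broken:

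- Define the set for the patency outcome as patients with proximal cerebral artery occlusion on pre-randomisation CT angiography, analysed by allocated arm whether or not an intervention was done.
- Count an artery open at the first procedural angiogram as patent. Also use any centrally read vessel imaging that was obtained for clinical reasons after allocation and before any intervention.
- Report by arm the numbers without baseline CT angiography and the numbers without early vessel imaging. For the latter, give best/worst-case bounds, with opposite values in the two arms for the difference.
- Label the comparison restricted to treated patients as descriptive, without a between-arm test.
- Do not substitute the 24±6 hour angiography. It comes after any intervention and answers a different question.

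The cost is wording only, with no new patients or scans. Patients without baseline angiography leave the set; that loss precedes allocation, so it does not break the comparison between arms. The bounds may be wide or uninformative if many patients have no early vessel imaging. If the SAP or imaging protocol already defines this set, a cross-reference is enough.
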